#### 8.4.9.5 Laboratory safety analysis

Laboratory safety variables will be summarised using descriptive statistics. Absolute values and changes from baseline will be tabulated. The values will be also categorised into low, normal and high according to their reference ranges. Clinically significant changes from baseline will be tabulated for some specific laboratory assessments, if applicable.

#### 8.4.9.6 Analysis of prior and concomitant treatments

Prior and concomitant treatments will be coded using the anatomical therapeutic chemical (WHODrug) classification system. Concomitant treatments during the study treatment period and at the EOS visit are tabulated separately.

#### 8.4.9.7 Other observations related to safety

Body temperatures and changes from baseline will be listed by patient and time point.

Possible special situations with study treatment, pregnancy data, and physical examination findings will be listed. Descriptive statistics for adrenal gland size with percent changes will be presented (Part 1 only).

#### 8.4.9.8 Analysis of the symptom questionnaire

All data received from digital symptom questionnaire will be summarised using descriptive statistics. The potential association between questionnaire symptom and signs data and other study data, e.g. adverse event, will be determined, where feasible.

## 8.5 Interim analyses

No formal interim analysis is planned in the study. However, in Part 1 the SMB will review the accumulating data (section 3.3.2 and the SMB charter). In Part 2, Simon's two-stage will be used for patients without AR LBD mutations. Criteria for continuation of patient enrolment may be met at any time during the conduct of the study. However, if not met, an interim analysis will be conducted after 23 patients are enrolled in the first stage and have had at least 8 weeks of follow-up, to assess the antitumor effects.

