#### Analysis of efficacy – antitumour effects

PSA: PSA data will be analysed descriptively by doseand study part. The number of responders (30% and 50% decline from baseline) at 12 weeks will be presented. Also number of patients with decrease in PSA from baseline will be tabulated by time point and by best response.

Soft tissue response: The frequency of responders according to RECIST 1.1 criteria of soft (target and non-target) lesions will be presented. Descriptive statistics of sum of lesion diameters and percent changes will be presented. ORR will be tabulated with descriptive statistics. ORR will be presented as best response and by time point.

Bone: Bone progression (PCWG3) and the changes from baseline in the number of lesions on bone scan will be reported as "no new lesions" or "new lesions".

CTC response will be tabulated with descriptive statistics.

ECOG performance status and time to ECOG deterioration: The ECOG performance status changes from baseline will be reported with descriptive statistics. Time to ECOG deterioration will be summarised by Kaplan-Meier method.

Clinical disease progression: Clinical disease progression symptoms will be summarised.

Time to disease progression: Median time to both PSA progression (deaths censored) and radiographic progression with RECIST 1.1 and PCWG3 criteria (deaths censored) will be summarised with descriptive statistics and Kaplan-Meier method.

Duration of objective response will be summarised with descriptive statistics.

rPFS will be summarised with descriptive statistics and Kaplan-Meier method.

Time on treatment: The time from the start of ODM-208 treatment until discontinuation of ODM-208 treatment will be summarised with descriptive statistics and Kaplan-Meier method, if appropriate.

Overall survival will be summarised with descriptive statistics and the Kaplan-Meier method.

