# 8.2 Estimation of sample size

No formal sample size calculation was performed. Separate dose escalation (3+3) will be performed in Part 1A Group 1 and Part 1A Group 2.

The purpose of the extension to the phase 2 expansion, introduced in Amendment 12, will be to achieve 2 cohorts of approximately 60 subjects per cohort under phase 2 conditions with and without AR LBD mutations to enable more accurate estimate of PSA response and rPFS, to support phase 3 study design as well as giving balance between the AR LBD mutation negative and positive patient population.

Simon's two-stage design (Simon R, 1989) was used to estimate the number of AR LBD mutation negative mCRPC patients in Part 2 extension (added in Amendment 12). The null hypothesis that the true PSA response rate is 5% will be tested against a one-sided alternative. Criteria for continuation of patient enrolment may be met at any time during the conduct of the study. However, if not met, then in the first stage, 23 subjects will be enrolled. If there are one or fewer PSA responses in these 23 subjects, the study will be stopped, otherwise, enrolment will continue as planned. The null hypothesis will be rejected if six or more PSA responses are observed in 56 patients. This design yields a significance level of 0.05 and power of 80% when the true response rate is 15%.

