#### 8.4.3 Analysis of efficacy

#### 8.4.3.1 Analysis of antitumour effects

#### 8.4.3.1.1 PSA

PSA data will be analysed descriptively by dose. Best response and the number of responders (30% and 50% decline from baseline) will be presented, and percentage of change from baseline will be tabulated by time point and by dose.

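### The Simon rule for the mutation-negative cohort has no stated PSA response window, and its stage-1 look may come after only 8 weeks, so the 80% power is not assured

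*Protocol*

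**What the plan says.** All references are to the protocol.

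- **Section 8.2** gives the design for the mutation-negative patients: "The null hypothesis that the true PSA response rate is 5% will be tested against a one-sided alternative". In stage 1, "in the first stage, 23 subjects will be enrolled"; then "If there are one or fewer PSA responses in these 23 subjects, the study will be stopped". At the end, "The null hypothesis will be rejected if six or more PSA responses are observed in 56 patients". The stated operating characteristics are a significance level of 0.05 and 80% power at a true rate of 15%. No time window is attached to the response being counted.
- **Section 8.5** times the look: "an interim analysis will be conducted after 23 patients are enrolled in the first stage and have had at least 8 weeks of follow-up". Sections 8.2 and 8.5 both allow the criterion for continuing to be met at any earlier moment.
- **The synopsis**, under analysis of efficacy, says: "The number of responders (30% and 50% decline from baseline) at 12 weeks will be presented". It also mentions best response.
- **Section 8.4.3.1.1** says: "Best response and the number of responders (30% and 50% decline from baseline) will be presented". No week is given.
- **Section 6.2.1.1** has PSA drawn in Part 2 on Day 1 and at Weeks 2 and 4, then every 4 weeks to Week 24 and every 12 weeks after that.

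**The concern.** A Simon design counts one binary outcome, fully observed, at both stages. Here the outcome has no fixed window, and the stage-1 count may be closed at 8 weeks although PSA continues to be measured. Both responder summaries that the protocol names, week 12 and best response, run past 8 weeks. A patient whose first qualifying decline is seen at week 12 could count as a failure at the look and a success at the end. The stated operating characteristics make no allowance for that.

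With a cut of one response, a single unseen responder can decide whether the cohort closes. The cohort was added to estimate PSA response and rPFS in mutation-negative patients and to support phase 3 design (sections 1.2.1 and 8.2). A false stop would defeat that purpose.

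**Working it through.** **Inputs.** From section 8.2: null rate 5%, alternative 15%, stage-1 size 23, stop at ≤1, final size 56, reject at ≥6. From section 8.5: at least 8 weeks of follow-up at the look. Two inputs are not in the protocol and are assumptions here: the share L of eventual responders who first respond after the look, and the number m of the 23 whose follow-up is still short.

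**Step 1: reproduce the stated design.** Let X1 ~ Bin(23, p) and X2 ~ Bin(33, p), since 56 − 23 = 33.

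- P(stop) = (1−p)^23 + 23·p·(1−p)^22
- P(reject) = sum over x ≥ 2 of P(X1 = x)·P(X2 ≥ 6 − x)

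At p = 0.15, P(stop) = 0.85^23 + 23 × 0.15 × 0.85^22 = 0.0238 + 0.0966 = 0.120, and power is 0.8003. At p = 0.05, P(stop) = 0.679 and alpha = 0.04996. The protocol's figures are confirmed.

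**Step 2: all 23 read at 8 weeks.** If each eventual responder is visible with probability 1 − L, the visible count is Bin(23, p(1−L)). At p = 0.15:

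- L = 10%: visible rate 0.135; P(stop) = 0.865^23 + 23 × 0.135 × 0.865^22 = 0.0356 + 0.1278 = 0.163
- L = 20%: visible rate 0.12; P(stop) = 0.88^23 + 23 × 0.12 × 0.88^22 = 0.0529 + 0.1658 = 0.219

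Power sums over the true stage-1 count x: P(X1 = x) × P(at least 2 of the x visible) × P(X2 ≥ 6 − x). Late responders still count at the final test.

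**Step 3: staggered entry.** Eight weeks is a minimum. Against a 12-week window, only patients enrolled within about 4 weeks of the last stage-1 entry are still short. The loss L is then applied to m of the 23 only.

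| Patients short of the window (m) | L | P(stop), p = 0.15 | Power, p = 0.15 | Alpha, p = 0.05 |
|---|---|---|---|---|
| any | 0 | 0.120 | 0.800 | 0.050 |
| 4 | 10% | 0.127 | 0.795 | 0.049 |
| 4 | 20% | 0.134 | 0.790 | 0.049 |
| 8 | 10% | 0.134 | 0.790 | 0.049 |
| 8 | 20% | 0.149 | 0.779 | 0.047 |
| 12 | 20% | 0.165 | 0.766 | 0.046 |
| 23 | 10% | 0.163 | 0.767 | 0.046 |
| 23 | 20% | 0.219 | 0.722 | 0.042 |

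**Step 4: effect of the endpoint definition.** Under best response, an unseen late responder can only lower power and alpha. Responses after week 12 are missed as well, so staggered entry helps less. Under a strict week-12 status, a transient response at week 8 adds to the stage-1 count. With all 23 read early, 3% of final non-responders showing such a response and none late, power is 0.828 and alpha 0.054. With 3% transient and 20% late, power is 0.780.

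**The case against.** The strongest reply is that no loss of power has been shown. The design reproduces exactly, any shortfall depends on a late-responder share that the protocol does not give, and 8 weeks is a floor that most stage-1 patients may well exceed. All of this stands. A reader might infer that the design fails to deliver 80% power; the documents do not support that, only that it is not assured. The direction is also uncertain under a strict week-12 status (step 4).

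Next, the 12-week and best-response figures are descriptive summaries, and neither is named as the Simon endpoint. Reporting several summaries is not a contradiction. That too stands, but it leaves the test with no stated window. The unseen SAP may supply one, and the decline threshold as well, since section 3.3.7 ties PSA response to PCWG3. The 8-week minimum and the power claim, however, are fixed in the protocol itself. If the SAP adopts either window that the protocol uses, the 8-week minimum is too short for it.

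Two stronger readings should not be pressed:

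- **Early leavers.** The follow-up condition could be taken to drop patients who die or leave before 8 weeks. It reads more naturally as a timing trigger: section 8.2 counts responses among the 23 enrolled, and section 8.3 makes ITT primary in Part 2.
- **Scope of the stop.** The wording in 8.2 could be taken to close the mutation-positive cohort too. The paragraph concerns mutation-negative patients, and 8.5 limits the rule to them. This is editorial.

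Finally, Part 2 is largely descriptive, and week 8 is a scheduled PSA visit. This limits the weight of the point but leaves a go/no-go rule without a response window.

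**Conclusion.** The point holds in a conditional form. The Simon rule lacks a response window, and its stop decision may be taken on less follow-up than either responder summary in the protocol needs. The 80% is right as arithmetic and rests on every stage-1 responder being visible at the look.

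If 10–20% of responders are late, power at 15% is about 0.77–0.72 with all 23 read at 8 weeks, and about 0.79–0.78 with 8 of 23 short of a 12-week window. The corresponding wrong-stop probabilities are 0.16–0.22 and 0.13–0.15, against 0.12 as designed. The late share and the number under-followed are assumptions. The risk is a false stop; under best response there is no inflation of false positives.

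**What to change.** In sections 8.2 and 8.5, define one PSA response for the Simon test and use it at both stages. One workable version is a decline of at least 50% from baseline at any time up to week 12, with non-evaluable patients counted as non-responders. Take the stage-1 stop decision only when each of the 23 mutation-negative patients has reached week 12 or left earlier.

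Two alternatives would also serve: keep the 8-week look and use an 8-week response window at both stages, or keep the present timing and restate the operating characteristics under it.

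As an editorial change, say in 8.2 that enrolment of the mutation-negative cohort, rather than the study, will be stopped.

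The cost is wording, plus a look that moves by up to about 4 weeks. Even that delay arises only if fewer than two responses have been seen, because continuation may be declared as soon as the criterion is met.

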# 9. DATA QUALITY ASSURANCE

# 9.1 Training

An investigator meeting or initiation meeting will be arranged for the investigators and other relevant study centre personnel. This meeting will include a review of the protocol, CRF completion and study procedures.

The investigators will ensure that appropriate training relevant to the study is given to the medical, nursing and other personnel involved in the study. The investigators will also ensure that any information relevant to the conduct of the study is forwarded to other relevant study centre personnel.

# 9.2 Case report forms

Electronic queries about missing, misleading, incomplete or illogical data will appear in the EDC system. An audit trail within the system will track all changes/corrections made. The investigator has to confirm the content of the eCRF with an electronic signature.

# 9.3 Monitoring, audits and inspections

The study monitor will visit the study centre regularly as agreed by the investigator and the sponsor. The study monitor will ensure that the study complies with GCP and applicable regulatory requirements and that the protocol is followed in all aspects, including the randomisation procedure, accurate recording of results, reporting of AEs, drug accountability and record keeping. Furthermore, it will be verified that the clinical facilities remain appropriate,

and that the CRFs correspond with source data. Further details regarding monitoring are presented in the monitoring manual.

The study may be audited by independent representative(s) of the sponsor or inspected by the competent authorities (CAs). For these purposes, the study monitor, auditors and inspectors will be allowed direct access to hospital or patient records/source data of the study subjects, original laboratory data etc., as far as they are related to the study.

It is essential that the investigator and other relevant members of the study centre team are available during the monitoring visits, audits and inspections, and that they devote sufficient time to these processes.

# 9.4 Laboratories and other vendors

Details regarding laboratory measurements and ECG analyses are presented in the separate instructions. Quality certificates are required from all safety laboratories.

Bioanalytics and metabolite screening will be performed in accordance with the principles of good laboratory practises (GLP) and GCP. Bioanalytics and steroid measurements will be performed using validated methods.

# **10.** FURTHER REQUIREMENTS AND GENERAL INFORMATION

## **10.1 Investigators and study administrative structure**

#### 10.1.1 Investigators

Should the investigator transfer one of his/her responsibilities to other members of the study centre team, he/she must have this documented.

In the event of changes in key study centre team members, the responsible investigator must ensure that the successor is fully informed and capable of following the procedures.

A curriculum vitae in English must be available from all investigators who sign the protocol, and from other relevant persons.

#### 10.1.2 Safety monitoring board (SMB)

A SMB will be established for the study. The duty of the SMB is to protect the ethical and safety interests of the study subjects and all others who may possibly be exposed to study treatments.

The SMB will include principal investigators from study centres taking part in Part 1 and the external endocrinologist. The SMB support group will include representatives from the sponsor and the clinical CRO. The SMB support group members may attend the SMB meetings but do not have voting rights. The voting rights are extended to the principal investigators only.

The sponsor will provide the SMB with mutually agreed safety, pharmacokinetic and antitumour activity data.

To ensure that the safety data generated during the study are received by all study centres, the principal investigator at each centre in phase I will be a member of the SMB. All investigators, including co-investigators, will receive all SUSAR reports on an ongoing basis throughout the study. In addition, full listings of all safety data, including CIOMS reports of all SAEs, will be made available for the SMB members before each formal cohort SMB meeting.

In Part 2, investigators who participated in the SMB during Part 1 will review safety data periodically.

Further details regarding the composition and responsibility of the SMB are presented in the SMB charter and section 3.3.2.

## 10.2 Insurance

The sponsor will provide clinical trial liability insurance for study subjects in all participating countries according to local regulations.

# **10.3 Retention of records**

The investigator agrees to keep the following documentation in the investigator's study file: patient records, including a subject screening log, a subject identification list, all original signed IC forms, a copy of CRFs and records of drug dispensing.

The study files at the study centres will be stored in the respective archives for 15 years, after which the sponsor will be contacted and the possibility of future archiving will be mutually agreed upon.

# **10.4 Completion of the study**

## 10.4.1 Completion of the study

The end of the study is defined as the date of the last subject's last visit or last contact with the study site.

Study centres will be closed upon study completion. A study centre is considered closed when all required documents and study supplies have been collected and a study completion/termination visit has been performed.

#### **10.4.2 Premature discontinuation of the study**

The sponsor reserves the right to prematurely terminate the study for valid scientific or administrative reasons. After such a decision, the investigator must contact all participating study subjects within 7 days, and invite them for an EOS visit. At this visit, all delivered study treatments and other study materials must be collected. All CRFs must be completed up to the EOS visit.

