#### 3.3.5.2 Dose modifications of corticosteroids

#### 3.3.5.2.1 Dose modification of glucocorticoid and mineralocorticoid replacement therapy due to under-replacement

The early identification of inadequate replacement therapy is essential for the safety of patients in the study. Guidance on the management of adrenal insufficiency is presented in Appendix 2A and measures to prevent adrenal crisis in Appendix 2B. Further, the IC and the diary contain guidance for the patient when to contact the study personnel in the event of possible symptoms. Study personnel will receive training from an endocrinologist at the start of the study in identifying and treating possible adrenal insufficiency and a flowchart is provided to guide clinical decision-making (see Appendix 2C, added in Amendment 7). Moreover, the fludrocortisone starting dose will be increased to 100  $\mu$ g in Phase 2. The digital symptom questionnaire (see section 6.5.4.7) will be trialled in the first 40 patients enrolled in Part 2 as a possible means to identify early indications of inadequate replacement therapy in future studies (note: the digital symptom questionnaire will not be used in France) but not in subsequent

patients. An emergency kit is also provided to each patient for emergency use in case of suspected adrenal crisis.

For safety reasons and if clinically indicated, dose adjustment including changes in dosing frequency of replacement therapy or switch to another glucocorticoid may be done at the discretion of the investigator.

During periods of increased stress, such as mild/moderate illness/flu (fever under 38°C), pain, strenuous physical activity, hot weather, accident, emotional stress, where an increase in endogenous cortisol is needed, the replacement therapy dosing may be inadequate. Patients will be instructed that on the first signs of illness they should immediately take an additional dose of steroid replacement therapy and subsequently contact the investigator for further guidance. If the patient cannot take the steroid replacement for any reason, such as vomiting, they should seek immediate hospital care for parenteral steroid replacement.

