Monitoring of replacement dose is mainly based on the clinical assessments of patient's symptoms and the clinical status including the weight, the BP and electrolytes. Patients and their family members should be educated for the event of possible acute or chronic signs of underreplacement. If corticosteroid deficiency is suspected to occur, patients should contact the study site without delay for additional instructions including follow-up and management plan. The study personnel should have a low threshold to suspect adrenal insufficiency, in order to prevent development of adrenal crisis. Additional replacement (doubled or tripled the dose of glucocorticoid and/or increased fludrocortisone dose and/or increased consumption of electrolyte containing fluids) should be considered whenever the patient reports persisting, new or worsened symptoms or signs above or in the event of unexplained electrolyte disturbance or has concurrent illness or injury. Acute illness or illness should routinely lead to temporary increases in replacement doses. An unscheduled follow-up visit including further symptom and clinical status evaluation, weight, BP, and electrolytes may be required. If the condition deteriorates despite these actions, or if the absorption of the replacement therapy is inadequate, such as during vomiting and diarrhoea, the patient should be instructed to use the emergency kit with parenteral (intramuscular) hydrocortisone according to institutional hospital guidelines or instructions provided by the sponsor. If the injection of parenteral hydrocortisone remains unsuccessful or impossible, up to 10 oral hydrocortisone tablets (10 mg), provided in the emergency kit, can be used in these situations as emergency. Immediately after the use of the emergency kit the patient must seek emergency hospital care. Patients with acute illness and fever over 38°C should always be admitted to the hospital directly.

Patients should carry steroid emergency card stating that they take glucocorticoid and mineralocorticoid daily. It is recommended that patients keep a small supply of glucocorticoid medication with them at all time.

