# 3.3.6.1 Discontinuation of replacement therapy

The time needed to taper down corticosteroids is individual and depends on the duration of adrenal gland suppression. Prolonged suppression may lead to adrenal gland atrophy that may take from a few weeks to several months to recover. Tapering down replacement therapy will be monitored during post-treatment period (see Section 6.1.6).

The glucocorticoid and mineralocorticoid replacement therapy should be withdrawn gradually and with caution avoiding secondary adrenal insufficiency.

The patient will be instructed that during stressful situations, such as fever, infection, trauma, surgery or mental stress, the glucocorticoid replacement dosing may be inadequate and extra substitution may be needed (information included in the IC and the diary).

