# 5.2 Auxiliary medicinal products (AMPs)

Active ingredient	Dexamethasone
Pharmaceutical form:	Tablet
Source:	Commercial
Unit strength:	0.5 mg and 1 mg
Posology:	Once daily
Route of administration:	Oral administration
Duration of treatment	Until discontinuation of ODM-208, after which dexamethasone dose is gradually decreased, see section 3.3.6.1

If 0.5 mg tablets are not available, the 1 mg dexamethasone tablet is scored and can be broken in half to give two 0.5 mg dose units.

Active ingredient	Fludrocortisone
Pharmaceutical form:	Tablet
Source:	Commercial
Unit strength:	50 μg or 100 μg
Posology:	Once daily
Route of administration:	Oral administration
Duration of treatment	Until discontinuation of ODM-208, after which fludrocortisone dose is gradually decreased, see section 3.3.6.1

Active ingredient	Hydrocortisone
Pharmaceutical form:	Tablet
Source:	Commercial
Unit strength:	10 mg
Posology:	Part 1: Three times daily
	Part 2: Included in the emergency kit
Route of administration:	Oral administration
Duration of treatment	Until discontinuation of ODM-208, after which hydrocortisone
	dose is gradually decreased, see section 3.3.6.1.

Active ingredient	Part 1: Prednisone
Pharmaceutical form:	Tablet
Source:	Commercial
Unit strength:	5 mg
Posology:	Twice daily
Route of administration:	Oral administration
Duration of treatment	Until discontinuation of ODM-208, after which prednisone dose is gradually decreased, see section 3.3.6.1.

Active ingredient	Part 1: Prednisolone
Pharmaceutical form:	Tablet
Source:	Commercial
Unit strength:	5 mg
Posology:	Twice daily
Route of administration:	Oral administration
Duration of treatment	Until discontinuation of ODM-208, after which prednisolone
	dose is gradually decreased, see section 3.3.6.1.

Active ingredient	Part 2: Hydrocortisone (emergency kit)
Pharmaceutical form:	Powder and solution, for solution for injection
Source:	Act-o-Vial, commercial
Unit strength:	100 mg
Posology:	Emergency case
Route of administration:	According to provider's instructions
Duration of treatment	Until end of adrenal follow-up period

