Blood samples for androstenedione, DHEA-S, pregnenolone/other steroids 			x	x			x				x						x 	x 	
Blood sample 1 for explorative ctDNA analyses			х														х		
Blood sample 2 for explorative ctDNA analyses			х						x			x		x	x		x		
Blood sample for CTC count 			х								х								
Blood sample for AR-V7 on CTC 			х																
Blood sample for explorative plasma			х		х	x	x												
Blood sample for germline DNA and PG			х																
Radionuclide bone scan		x 							x 			x 		x 	x 				
Chest, abdomen and pelvic CT or MRI		x 							x 			x 		x 	x 				
Dispense ODM-208 and replacement treatment			х				х		х		х	х	х	х	х				
Dispense emergency card and hydrocortisone emergency kit			x																
Return study treatment							x		x		x	х	х	х	х		х		
Dispense/return diary card			x	х	x	x	x	x	x	x	x	x	x	x	х		х		
Digital symptom questionnaire (voluntary) 		×	x 																
AEs, concomitant treatments and current medical conditions		х																	

Visit	Pre- screening	Screening	1	2	3	4	5	6	7	8	9	10	11	12	13, 14 etc.	Post- treatment visit	EOS	Follow -up 	Sur- vival 
Day		-21 to -1	1	8	15	22	29	43	57	71	85	113	141	169	253, 337 etc.	+14	+28		
Window (days)				± 2							$\pm 4$					± 2	± 4		±14
Week				1	2	3	4	6	8	10	12	16	20	24	36, 48 etc.				Every 12 wks
Survival status		X																	X

Depending on time needed to taper down glucocorticoid and mineralocorticoid treatment.

 After meal

 Telephone calls on Day 5, 12, 19, 26, 36 (week 5) and 50 (week 7)  $(\pm 1)$ 

3 registrations 1-2 min apart

 Only electrolytes

 Every 3 months until 6 months, thereafter every 6 months

 Pregnenolone and DHEA-S

 Previous scans can be used as the baseline assessment if they were performed within 4 weeks prior to the start of the study treatment

 Performed within 1 week before the actual visit (results must be available at the visit)

 Local laboratory analysis

 Central laboratory analysis

 For TSH, PSA and testosterone, screening samples are analysed at the local laboratory, whereas the samples from Visit 1 onwards are analysed at the central laboratory

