# 6.1.6.2 Part 1/Phase 1 and Part 2/Phase 2: End-of-study (EOS) visit

Patients will have an EOS visit 28 (+/-4) days after the last dose of ODM-208 treatment. The following procedures will be performed at the EOS visit:

• Physical examination, body temperature, and weight

- BP, HR and 12-lead ECG
- Orthostatic test (Part 1 only) •
- Safety laboratory assessments: haematology, chemistry and urinalysis. Blood for HBA1c • for patients with diabetes. Blood samples for dexamethasone and fludrocortisone analysis.
- Determination of PSA concentration •
- Exploratory ctDNA analyses •
- Pregnenolone and DHEA-S determinations •
- Drug accountability
- AEs, concomitant treatments and current medical conditions •
- Return diary card •

Corticosteroid substitution will be continued according to the instructions in section 3.3.6.1.

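### After sponsor termination, Section 10.4.2 read literally takes back the Part 2 hydrocortisone emergency kit at the EOS visit, while Section 5.2 keeps it until adrenal follow-up ends

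*Protocol*

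**What the plan says.** **Termination rule.** If the sponsor stops the study, Section 10.4.2 has the investigator contact patients within 7 days and invite them to an EOS visit. It continues: "At this visit, all delivered study treatments and other study materials must be collected". CRFs are then completed up to that visit.

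**The kit.** Section 5.2 lists the Part 2 injectable hydrocortisone 100 mg emergency kit among the auxiliary medicinal products, with duration "Until end of adrenal follow-up period". Section 3.3.5.2.1 gives its purpose: "An emergency kit is also provided to each patient for emergency use in case of suspected adrenal crisis".

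**Follow-up after EOS.** Under Section 6.1.6.3 and Table 7, a patient who still needs a glucocorticoid or mineralocorticoid at EOS has visits at 4 and, if needed, 8 weeks, then calls at 16 and, if needed, 24 weeks. On recovery, Section 3.3.6.1 says: "Prolonged suppression may lead to adrenal gland atrophy that may take from a few weeks to several months to recover".

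**Routine EOS.** Section 6.1.6.2 lists drug accountability and "Return diary card", and continues corticosteroid substitution. Table 3 has a row "Dispense emergency card and hydrocortisone emergency kit" but none for returning either item.

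**The concern.** Section 10.4.2 makes collection at EOS complete and mandatory, whereas Section 5.2 leaves the injectable kit with the patient beyond EOS for as long as adrenal follow-up lasts. For a Part 2 patient still on replacement at EOS, a site that takes both sections at their word cannot comply with both.

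The stake is patient safety. The kit is the rescue injection for a suspected adrenal crisis, including when vomiting or diarrhoea prevents absorption of oral steroids. Continued oral replacement is therefore not a full substitute. A literal reading of Section 10.4.2 removes the injection while the adrenal glands may still be suppressed. No endpoint, sample size or analysis depends on this.

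**Working it through.** No figure in the protocol needs reproducing. The check is a comparison of sections, followed by one line of arithmetic.

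**Step 1. Does Section 10.4.2 reach the kit?** It has two categories.

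- *Study treatments.* Usage elsewhere favours a narrow sense, close to ODM-208. Section 5.9 asks for all study treatment packages back at every visit, which cannot include a rescue kit that the patient must hold. Section 6.1.5.1.1 names treatment containers, diary, emergency card and kit as separate items, and speaks of a dose of study treatment plus dexamethasone. On the other side, the kit is listed in Section 5, whose title is Study Treatments. This category alone does not settle the matter.
- *Other study materials.* The phrase is undefined and carries no exception. The kit is dispensed by the study, so it falls within the ordinary meaning whichever way the first category is read.

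**Step 2. Does another section exempt termination?** Section 4.5 lists termination by the sponsor as a reason for discontinuation, refers to Section 10.4, and then requires glucocorticoid and fludrocortisone to continue after ODM-208 stops. Section 6.1.6.3 applies to anyone still needing replacement at EOS, with no limit for termination. Neither mentions keeping the kit. Section 5.2 does, but Section 10.4.2 does not refer to it.

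**Step 3. Is the routine EOS visit also in conflict?** No. Section 6.1.6.2 and Table 3 require no return of the kit. Section 5.9 collects remaining treatments at the end of the study, which Section 10.4.1 defines as the last subject's last visit or contact. Only Section 10.4.2 ties collection of everything to EOS.

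**Step 4. Size of the gap per patient.** Inputs are the contact weeks in Table 7. Gap in days = weeks of adrenal follow-up after EOS × 7.

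| Follow-up ends at | Gap, if follow-up continues after termination |
|---|---|
| EOS (off replacement) | 0 |
| 4 weeks | 4 × 7 = 28 days |
| 8 weeks | 8 × 7 = 56 days |
| 16 weeks | 16 × 7 = 112 days |
| 24 weeks | 24 × 7 = 168 days |

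If termination instead ends adrenal follow-up at EOS, the period in Section 5.2 ends there too and the gap is 0 in every row.

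**Step 5. Scope.** The extended duration in Section 5.2 is stated for the Part 2 injectable product only, so Part 1 is not counted.

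**The case against.** The strongest reply is that this is general administrative wording and that the specific rule in Section 5.2 governs the product. The narrow use of study treatment shown in Step 1 supports that, and the diary is an obvious example of what other study materials might mean. A sensible site might well leave the kit with the patient. What stands of this is that the conflict is less sharp than one between two specific instructions. It does not go away, because Section 10.4.2 admits no exception and nothing shown tells the site which section prevails.

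A second reply is that CRFs are completed only up to EOS, so follow-up may be meant to stop there and the two durations would then coincide. The text permits that reading, and the day counts above depend on rejecting it. Even so, a patient still suppressed would then leave with neither kit nor follow-up, which sits badly with Sections 4.5 and 6.1.6.3. The section needs clarifying on either reading.

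Third, Appendices 2A to 2C are listed but not shown, and 2B, on preventing adrenal crisis, might deal with kit handling. That remains unknown. The injectable is also a commercial product, so trial supply need not be the only source.

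Some stronger readings are tempting but unsupported:

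- *Section 10.4.2 stops replacement steroids.* It does not. Sections 4.5 and 6.1.6.2 continue them.
- *It plainly removes the emergency card and oral steroids as well.* The wording reaches them by implication only. Section 3.3.5.2.1 says "Patients should carry steroid emergency card stating that they take glucocorticoid and mineralocorticoid daily", but no retention period for the card is stated.
- *About 120 patients (60 + 60 planned in Part 2) are exposed.* Patients whose EOS visit is already past cannot lose a kit at a future one, and Section 6.1.6.4 provides for subjects whose EOS preceded Amendment 12. The protocol gives no basis for any count.

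**Conclusion.** The inconsistency is real but minor. Read literally, Section 10.4.2 recalls the Part 2 injectable hydrocortisone kit at EOS, while Section 5.2 keeps it until the end of adrenal follow-up. It matters only if the sponsor ends the study early, only for Part 2 patients still on replacement at that visit, and only if a site applies the collection rule literally.

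The gap per affected patient lies between 0 and 168 days. The upper end is a ceiling: it assumes that follow-up under Section 6.1.6.3 continues after termination and runs to its last contact, whereas Section 1.3.2 expects replacement to be needed for several weeks. The number of patients affected cannot be derived. The case for acting is that the item is a rescue medicine and the correction is nearly free.

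**What to change.** Add one sentence to Section 10.4.2 at the next amendment, for example: *For patients who still need corticosteroid replacement at this visit, adrenal-recovery follow-up continues under Section 6.1.6.3, and the hydrocortisone emergency kit, the steroid emergency card and replacement corticosteroids are exempt from collection until that follow-up ends.*

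The first half settles whether follow-up survives termination. The second removes the clash with Section 5.2; the card and replacement steroids are named for clarity only. Appendix 2B should be checked so that it says the same. No visit or assessment is added beyond those already in Table 7. The small downside is that some supplies are retrieved later.
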